## **STUDY VARIABLES**

Among the variables that are available for the present study are:

- Independent Variables: Sociodemographic characteristics, related to the disease or clinical condition and the CKD intervention.
- Dependent variables: Self-management behaviors, therapeutic adherence, and self-efficacy.

Within the mediating, shaping or confounding variables, the following are found according to what is established in the literature: age, gender, level of education, time of diagnosis and other comorbidities, which are initially considered independent variables and will be measured. In the study, for its management, strategies such as randomization will be used, the differences between the crude estimates of an association and those adjusted considering a confounding variable will be identified and its adjustment is responsible for at least 10% in the magnitude of the difference.

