## **METHODOLOGY**

This is a quantitative investigation, with a pragmatic randomized clinical trial (pRCT) design, parallel experimental type, given the one-to-one allocation in two parallel groups with repeated pre-test and post-test measures, considering that this type of study is useful for evaluating interventions in usual care (23). In CKD, the use of a pRCT enables a broader range of patients to be included to test an intervention applicable to patient care and to measure relevant patient-centered outcomes, thus improving external validity and translation of the results into the clinical care (24).

Where the outcome variables are: Self-management behaviors (primary), self-efficacy and therapeutic adherence (secondary). The population will be adult men and women with chronic kidney disease in stages 1-4, who attend control of their disease or belong to the BBraun Avitum Prevenser program.

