### **SAMPLE**

**Sample design:** The sample size was calculated through probability sampling, since individuals have the same probability of being chosen. On the other hand, of the comparison of means in independent groups, assuming a power of 80%, a confidence level of 95%, an expected mean difference of 18.13 in the improvement of self-management, reported by previous studies (6,27).

**Sample size:** A total of 82 participants (41 per group), in addition, a mortality of 20% of the participants is expected, so a total sample of 100 participants (50 per group) will be assumed. made in the Epidat 3.1 program.

**Randomization:** Participants will be randomized into two groups, using sequentially numbered opaque sealed envelopes, where the investigator and participants will be blinded to the allocation of each group. For the generation of the randomization sequence, it will be developed by the investigator by means of the realization of a table of random numbers in the Epidat 3.1 program to eliminate the selection bias, in the same way, said table will be verified to guarantee balance between the number of participants assigned to each group (control and intervention).

**Blinding:** In view of the need to minimize bias, both the participants and the recruitment research assistant will be blinded until allocation. The Result Research Assistant will not have access to the allocation base, nor to the allocation codes. On the other hand, it is

declared that the intervention will be given by the researcher and that the main researcher will also participate in statistical analysis, therefore, the study is classified as single blind.

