### **APPROACH TO THE ANALYSIS FRAMEWORK**

To respond to specific objectives 1 and 2, a statistical analysis will be carried out through descriptive statistics. Subsequently, a normality test will be carried out, to identify how the data distribution is presented, in addition, it is carried out to determine the tests to be used, whether parametric or non-parametric in the inferential analysis, bivariate and multivariate analysis. A bivariate analysis, to compare the sociodemographic and clinical characteristics between the groups.

To respond to specific objective 3, Inferential statistics will be carried out, which will be carried out to accept or reject the null or alternative hypothesis, which are proposed as:

- H1: The CKD SMS intervention in self-management in people with CKD in early stages is effective on self-management behaviors, self-efficacy, and therapeutic adherence. (H1: G1 > G2; p < 0.05)
- H0: The CKD SMS intervention in people with CKD in early stages is not effective on self-management behaviors, self-efficacy, and therapeutic adherence. (H0: G1 = G2; p > 0.05)

But it is also used multivariate analysis, to determine the individual relationship but also the relationship of the possible variables that intervene on the results, a simple logistic regression model will be built and adjusted according to the possible confounding variables.

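### The 10% change-in-estimate screen leaves the adjusted treatment estimate undefined until outcomes are seen, and gives up some precision

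*Combined protocol and SAP*

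**What the plan says.** The METHODOLOGY section describes a randomised trial, "given the one-to-one allocation in two parallel groups with repeated pre-test and post-test measures", with self-management behaviours as the primary outcome.

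STUDY VARIABLES lists possible mediating or confounding variables: "age, gender, level of education, time of diagnosis and other comorbidities, which are initially considered independent variables and will be measured". For handling them it relies on randomisation and adds that "the differences between the crude estimates of an association and those adjusted considering a confounding variable will be identified", with the condition that "its adjustment is responsible for at least 10% in the magnitude of the difference".

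APPROACH TO THE ANALYSIS FRAMEWORK plans three relevant things:
- "A bivariate analysis, to compare the sociodemographic and clinical characteristics between the groups";
- a test of the two groups ("H1: G1 > G2; p < 0.05");
- a multivariate step in which "a simple logistic regression model will be built and adjusted according to the possible confounding variables".

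No section fixes the covariates, gives a cut-point for turning a score into a binary outcome, says whether the crude or the adjusted result is primary, or provides for adjustment by the pre-test score.

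**The concern.** A change-in-estimate rule is meant for observational data, where covariates may differ systematically between groups. Under randomisation they differ only by chance. On a mean-difference scale the rule therefore selects covariates by how unlucky the allocation was and by how small the crude effect turned out to be. It does not select them by how well they predict the outcome, which is what brings precision.

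Two things are at stake. First, the adjusted estimate is whatever the screen yields, so it cannot be specified before outcomes are seen. This matters more here because the SAMPLE and BIAS CONTROL sections have the main researcher both delivering the intervention and taking part in the analysis, unblinded. Second, precision available from data already being collected is partly given up.

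**Working it through.** **The plan's own figure.** SAMPLE gives 80% power, 95% confidence, a difference of 18.13 and 41 per group, but no SD, so 41 cannot be reproduced. Solving backwards, two-sided: d = (1.960 + 0.842) × √(2/41) = 0.62, so SD = 18.13/0.619 = 29.3. If one-sided, d = 0.55 and SD = 33.0. With 20% loss from 100, 80 complete (40 per arm), and 80% power corresponds to d = 2.802 × √(2/40) = 0.626. That is the effect assumed below.

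**Why imbalance drives the screen on a linear scale.** For one covariate with within-arm slope b and a difference Δ in covariate means between arms, crude − adjusted = b × Δ. The covariate passes when |b × Δ| ≥ 0.10 × |crude|. Working in SD units, take b = r (the correlation with outcome) and set crude at 0.62. Δ has standard deviation √(2/41) = 0.221.
- r = 0.5: it passes if |Δ| ≥ 0.062/0.5 = 0.124. P(dropped) = P(|Z| < 0.124/0.221 = 0.56) ≈ 0.43. Simulated: 44%.
- r = 0.3: threshold 0.207, P(|Z| < 0.94) ≈ 0.65. Simulated: 65%.
- r = 0.7: threshold 0.089, P(|Z| < 0.40) ≈ 0.31. Simulated: 31%.

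For r = 0.5, mean absolute imbalance was 0.26 SD when kept and 0.07 SD when dropped.

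**Dependence on the effect.** With 41 per arm and five candidates (assumed correlations 0.5, 0.3, 0.1, 0.1 and 0), the best predictor is dropped in 12%, 22%, 44% and 63% of trials at true effects of 0, 0.3, 0.62 and 1.0 SD. A pure-noise covariate, screened alone, is kept in 40% of trials at zero effect and in 6% at 0.62. At 0.62 all 32 possible covariate sets occurred, and the commonest accounted for 27% of trials.

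**Cost against a fixed set.** Linear model, 40 per arm, 4,000 trials per scenario, five independent covariates sharing the stated R² in proportions 50/25/15/7/3%. Each is screened singly, then the retained ones are fitted jointly.

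| Assumed R² | 10% | 25% | 40% |
|---|---|---|---|
| Strongest covariate dropped, effect 0.626 SD | 75% | 59% | 48% |
| Power, 10% rule | 81% | 85% | 90% |
| Power, fixed set | 81% | 87% | 93% |
| Mean model SE, rule relative to fixed | +1% | +7% | +14% |
| At least one confounder declared, no effect | 93% | 98% | 99% |

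A repeat run gave power of 80 v 80, 84 v 86 and 89 v 93%, so the loss is 0 to 4 points. The actual spread of the estimates widens less than the model SE: 0.207 v 0.198 at R² 25% (+5%) and 0.193 v 0.181 at 40% (+7%).

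**Type I error.** Under the rule it was 4.1% to 5.8% across these scenarios, and 4.2% in the 41-per-arm simulation. Taking the better of the crude and screened-adjusted results gave 5.8% to 7.2%.

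**Logistic version.** Outcome split midway between the arm means (assumed), 41 per arm, effect 0.62 SD, 10% change in log odds ratio: r = 0.5 is dropped in 28% of trials, r = 0.3 in 56%, and noise is kept in 13%.

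**The case against.** The strongest objection is that the only adjusted model the plan names is logistic. Odds ratios are non-collapsible, so adjusting for a strong predictor moves the log odds ratio even when the arms are balanced on it. Among trials with imbalance below 0.1 SD, a covariate with r = 0.5 was dropped in 21% under the logistic model against 94% under the linear one; with r = 0.7, 1% against 87%. A reader might infer that the plan will routinely discard its best predictor whenever that predictor is balanced. This holds on a mean-difference scale but not for the planned odds ratio, and the linear drop rates should not be carried over to it. It does not make the screen sound: it then reacts to non-collapsibility as well, and the covariate set is still chosen after outcomes are known.

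The harm is also modest. The highest drop rate, 75%, belongs to the scenario where dropping costs no power, and the rule still does better than no adjustment (84 v 78% at R² 25%, 90 v 79% at 40%). Both points stand.

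A reader might infer a false-positive problem. The rule by itself does not produce one. An error rate near 7% needs someone to emphasise the better of two results. No section proposes that, though none excludes it, since neither result is named primary.

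Finally, the sentence in STUDY VARIABLES is garbled and never says that covariates are retained. The change-in-estimate reading is an inference, though it is the only workable one. Nor does the plan link the baseline comparison between groups to the choice of covariates, so that link should not be asserted.

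**Conclusion.** The concern holds in this form: the plan states a data-driven screen, fixes no covariate set, and so leaves the adjusted estimate undefined until outcomes are seen, with some loss of precision. That the estimate is undefined follows from the text and needs no simulation. The size of the precision loss rests on assumptions: the effect in SD units, the R² values, the correlations, and the cut-point for the logistic version are none of them in the documents. Within the ranges tried, the power loss is 0 to 4 points. The documents do not support a claim of inflated type I error from the rule itself.

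One feature strengthens the point. The pre-test score, likely the best single predictor of the 16-week score, is not among the candidates, so the plan passes over it before any screening takes place. This is a change that should be made, not one that invalidates the trial.

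**What to change.** Delete the 10% screen. Before any outcome is seen, name one primary estimate: the arm difference from a linear model (ANCOVA) of the 16-week self-management score on arm, the pre-test score, and a short fixed list from STUDY VARIABLES (age, gender, education, time since diagnosis, comorbidity). Use that set whatever the imbalance. This takes the place of the logistic model as the adjusted analysis of the primary outcome. Define the coding now, numeric or with few categories; comorbidity in particular is open-ended as written. Report the unadjusted difference as supporting only. Describe baseline characteristics by arm without significance tests.

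The cost is SAP wording; the pre-test and the listed variables are already to be collected. The model spends about 1 (pre-test) + 1 (age) + 1 (gender) + 1 to 2 (education) + 1 (time since diagnosis) + 1 to 2 (comorbidity) = 6 to 8 degrees of freedom. With 80 completers this leaves 80 − 2 − 8 = 70 to 80 − 2 − 6 = 72 residual. That is small in a linear model if the coding stays compact; it would be less comfortable in a logistic model with perhaps 40 events.

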## **PHASES OF THE STUDY**

The phases of the study will be pre-pilot phase in which the CKD SMS intervention will be adapted to the Colombian context, considering the evaluation by experts in the management of people with CKD in early stages. Pilot phase will be carried out the exploration of the field, followed by adjustments regarding the application time in the handling of the instruments and the training in these aspects for the research assistant. And the main phase of the study where the intervention will be implemented and the data will be collected, the latter by means of the instruments: characterization sheet, Self-management instrument in early-stage chronic kidney disease CKD SM, EAT therapeutic adherence scale, Self-efficacy scale general. The intervention is planned to be implemented both in person and digitally assisted.

## **INTERVENTIONS**

### **- CKD SMS intervention**

CKD SMS (Chronic Kidney Disease Self-Management Support) intervention (6,27), guided by the Social Cognitive Theory, through the manipulation of self-efficacy, is educational for the adult with CKD in early stages where a primer will be used which contains a primer that explains the functions of the kidneys, the first signs and symptoms of CKD and the strategies to control or delay the progression of CKD, such as the benefits of maintaining a healthy lifestyle and adherence to treatment. Also, a diary for participants to record side effects of

medications, monitor their clinical data, treatment plan and questions for medical appointments.

All the materials of the intervention will be prepared for an appropriate reading level for the participants and will be delivered in physical or digital format, the intervention will be provided by the researcher who is a nurse, a master's degree in nursing with an emphasis on chronic patient care and with experience of 12 years, of which 7 have been in the management of people with CKD in the different stages and in renal replacement therapies such as hemodialysis, peritoneal dialysis and kidney transplantation.

The intervention begins with a face-to-face or digitally assisted session, entry into improving the knowledge and self-management of CKD through, using the four sources of manipulation of self-efficacy (achievement of performance, indirect experience, verbal persuasion, and self-evaluation). In this session, participants will be asked to identify their problems related to CKD and establish, based on these two goals, that they are real and achievable according to their priorities. These goals will be recorded in the monitoring format and will be monitored in the telephone or WhatsApp follow-ups. This using the performance achievement manipulation source, said session lasts 60 minutes, as does the final session at week 16 (6,27).

For the use of vicarious or indirect experience, images will be used that demonstrate what should or should not be done within the educational material, in addition to the use of videos of successful experiences. Verbal persuasion will be used through providing verbal advice and suggestions to each participant. Self-assessment will be used to encourage participants to identify where they have been successful in the management of CKD and therapeutic adherence, in addition to expressing difficulties and concerns in managing their disease (6,27).

The continuation of the intervention will be carried out through 2 follow-ups by phone or via WhatsApp with a duration of 20 to 30 minutes per week 4 and 12, where the research nurse will reinforce the self-management action plan and monitor progress towards the goals set; Therefore, the focus will be to identify improvements and encourage participants to continue with the change in behavior through positive reinforcement, in addition, discussion processes will be carried out according to the information given through the educational material given to the participant. The participant will be encouraged to seek family and social support to achieve long-term behavior changes, in addition to raising their concerns, doubts or concerns that arise during the intervention in each follow-up to be able to respond or, failing that, manage the resolution of these (6,27).

The intervention is carried out individually, digitally assisted both for the meetings and for the follow-up, always trying to promote a quiet environment, free of noise and in the time agreed with the participant to give the intervention.

### **- Conventional intervention**

The conventional intervention corresponds to the protocol established in the Prevenser program of the renal unit (BBraun Avitum) for the management of people with CKD in early stages.

## **BIAS CONTROL**

### **Internal validity**

**- Selection and performance bias:** to avoid this bias, random selection will be carried out by delimiting the population and defining the sampling frame in detail, being adequate for the study design; in addition to the generation of a list of the patients who attend the controls, for the assignment of random numbers and the appropriate method for this by means of a software. On the other hand, allocation concealment will be carried out with sealed envelopes containing the allocation number; Within the calculation of the sample, an additional 20% is initially added as prevention of losses in the groups, additionally the intervention protocol will be carried out faithfully and the largest portion of the contact data of the participants will be taken in order not to lose the contact and their participation in the follow-up.

**- Performance and arrest bias:** A single-blind study will be carried out in which the allocation to the participants will be blinded, since the intervention and the analysis of the results will probably have to be developed by the main investigator and therefore this cannot be blinded. But to have faithful results, the data collection (application of the instruments) will be supported by a research assistant who will also be blinded to the assignment of the participants to the control group or experimental group.

**- Attrition bias:** The collection of the information will be meticulous in order not to lose any data, and, in addition, a percentage addition will be made in the calculation of the sample to predict the mortality of the participants.

**- Reporting bias:** The delivery of the results without missing the expected results in accordance with the methodological approach, in the same way, will be its publication.

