- Respect: In this research, the use of informed consent by the participant will be guaranteed. In addition to other measures regarding the collection of data for which the participant will be identified with a code to safeguard their privacy and confidentiality, in this way their rights will be respected, and their dignity will be maintained, said number will be used in the instruments for collecting and analyzing information.
- Beneficence and non-maleficence: For this research, an exhaustive critical review of the best available evidence was carried out, which made it possible to select the intervention proposed by Havas et al. (27) and later by Nguyen et al. (19), in people with chronic

kidney disease in early stages. In addition, there are systematic reviews and meta-analyses of experimental studies that have demonstrated the benefits of interventions in self-management, on the other hand, if any risk condition is identified in the participant, the interdisciplinary treating group will be notified for its respective management.

- Confidentiality and Privacy: It will be safeguarded through the management of the information where the data will be supervised, controlled, and processed by the researcher and the identity of the participants will be assigned a code for their identification. The information will not be transferred to people who are not part of the investigation team.

- Veracity and Fidelity: It will be respected through the presentation of the research findings, where no type of manipulation will be carried out to obtain results.

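### The nurse-investigator who delivers the intervention is expected to take part in the analysis unmasked, with test and adjustment settled from the data; lock one primary analysis and run it on coded arms

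*Combined protocol and SAP*

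**What the plan says.** The section SAMPLE, under Blinding, states that "the intervention will be given by the researcher and that the main researcher will also participate in statistical analysis", and on that ground calls the study single blind. The CKD SMS intervention section adds that "the intervention will be provided by the researcher who is a nurse". The section BIAS CONTROL, Internal validity, treats delivery and analysis together: "the analysis of the results will probably have to be developed by the main investigator and therefore this cannot be blinded".

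Two further tasks fall to what reads as the same person. Of the randomisation sequence, the Randomization paragraph says "it will be developed by the investigator by means of the realization of a table of random numbers". Under ETHICAL CONSIDERATIONS, "the data will be supervised, controlled, and processed by the researcher".

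Outcome collection is protected: a masked assistant applies the instruments, and the results assistant is denied the allocation list and codes.

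On the choice of analysis, APPROACH TO THE ANALYSIS FRAMEWORK says of a normality test, which it does not name, that "it is carried out to determine the tests to be used, whether parametric or non-parametric in the inferential analysis". It then adds a logistic model adjusted for possible confounders. STUDY VARIABLES lists five candidate confounders and describes a comparison of crude and adjusted estimates in which "its adjustment is responsible for at least 10% in the magnitude of the difference".

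**The concern.** The plan gives one reason for leaving the analysis unmasked: the person who delivers the intervention will probably also analyse it. That reason covers delivery. It does not cover analysis, which needs only outcome data and two arm labels, and which someone else could run.

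The gap matters because the analysis is not fixed. An analyst who delivered the intervention and knows the arms may settle, without intending to, on the version that looks best for it. The 5% error rate applies to one analysis fixed in advance, not to the most favourable of several.

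**Working it through.** **1. Does the stated reason support the conclusion?** Masking delivery would require the nurse not to know who receives the sessions, which is impossible. Masking analysis requires only that whoever runs the model does not know which label is which arm. The first being impossible says nothing about the second. The protocol mentions no independent analyst, coded data file or locked plan.

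**2. What is left open?** The normality test is unnamed. The plan does not say whether the primary comparison uses post-test scores, change scores or a baseline-adjusted model. The final covariate set depends on the data. The logistic model has no cut-point, although the outcomes are scores. The reporting-bias paragraph promises complete reporting but fixes no model.

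**3. The plan's own figure.** No stated figure bears directly on this point. The 41 per group cannot be reproduced, because no SD is given. Solving for it with d = 18.13, 80% power and two-sided 5%:

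SD = d / [(z₀.₉₇₅ + z₀.₈₀) × √(2/n)] = 18.13 / [(1.960 + 0.842) × √(2/41)] = 18.13 / 0.619 = 29.3.

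This SD is used only in step 5.

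**4. Size of the risk under no effect.** From the documents: 41 per arm, 1:1 allocation, 5% level, five candidate covariates and the 10% rule. Assumed: two-sided testing, normal scores, baseline-outcome correlation 0.3, 0.5 or 0.7, each covariate correlated 0.2 with the outcome, and Shapiro-Wilk as the normality test. The six analyses are also an assumed list: t-test and Mann-Whitney on post-test, the same two on change, ANCOVA on baseline, and the 10%-rule adjusted model. There were 8,000 simulated trials per correlation.

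| Proportion of null trials | r = 0.3 | r = 0.5 | r = 0.7 |
|---|---|---|---|
| One locked ANCOVA, p < 0.05 | 4.8% | 5.1% | 5.1% |
| Normality test first, then t-test or Mann-Whitney | 5.0% | 5.3% | 5.5% |
| 10% rule applied as written | 4.8% | 4.9% | 4.6% |
| Smaller p of t-test and Mann-Whitney | 5.8% | 6.3% | 6.1% |
| Smallest p of six analyses | 11.7% | 13.1% | 13.7% |
| Locked ANCOVA, favouring the intervention | 2.0% | 2.5% | 2.3% |
| Best of six for the intervention, arms known | 5.5% | 6.9% | 6.7% |
| Smallest p of six, arms coded, happens to favour the intervention | 5.5% | 6.9% | 6.7% |

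The Monte Carlo standard error is √[p(1−p)/8000]: about 0.4 points at 12% and 0.2 points at 2.5%. Further simulations with 40 per arm and five analyses gave similar results for the smallest p: 12.5% (13.4% with skewed scores) in one, and 11.0-12.8% in another, with 5.6-6.4% favouring the intervention.

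Three things follow. The stated rules, followed mechanically, cost almost nothing. Choosing between the t-test and the rank test alone costs about one point. The excess comes from choosing freely across the whole list, and coding the arms leaves it unchanged.

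**5. Would coded labels stay masked?** At the planned effect, the probability that the higher-scoring arm is the intervention arm is Φ[d / (SD × √(2/n))]. With SD 29.3 and 41 per arm this is Φ(2.80) = 0.997. With SD 43.5, half the 29-116 score range and so the largest SD a score can have, it is Φ(18.13 / 9.61) = Φ(1.89) = 0.97. If the effect is as large as planned, the labels can be guessed.

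**The case against.** The strongest reply is that the plan's statement is close to true for this particular person. The investigator makes the sequence, has four contacts with each treated participant (opening session, weeks 4 and 12, final session at week 16) and processes the data. New numbers and A/B labels would not reliably hide the arms from someone who may recognise participants by their characteristics. This stands. It argues for having someone else run the primary analysis, not for leaving the analysis unmasked.

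A reader might infer that coded labels would remove the bias. The working does not support that: the error from picking the smallest p is the same with arms coded or named, and the labels may be guessed. A reader might also take 11-14% as the cost of unmasking, or as this trial's expected error rate. It is neither. It is the worst case of free choice over an assumed list, counts false results in both directions, and measures an unfixed model. Nor do the normality and 10% rules inflate the error by themselves.

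The wording on roles is hedged. One section says the main investigator will probably do the analysis; another says the main researcher will participate. Sole analysis by the deliverer is likely, not certain. The logistic model is an addition to the group comparison, not a declared alternative.

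Finally, asking the results assistant to recode the arms would conflict with that assistant's masking while post-tests, which the Schedule spreads over several months, are still running. That also stands, and it determines who should recode and when.

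**Conclusion.** The point holds in a limited form. The deliverer is expected to take part in an unmasked analysis, the reason given does not justify that, and the test and adjustment are left to be settled from the data. Under the assumptions in the working, free choice could raise false results favouring the intervention from a nominal 2.5% to about 5.5-7%, roughly two to three times. The proportion of null trials with some p below 0.05 would be about 11-14%. Correlations, list of analyses and two-sided testing are assumptions, and nothing in the documents shows that such selection would occur. Masked outcome collection is not in question. Locking the model is what controls the error rate; coding the arms is a useful second step that reduces the bias without removing it. The change is worth making before post-test data are seen.

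**What to change.** 1. Before any post-test data are seen, date a short plan that names one primary analysis, for example ANCOVA of the week-16 CKD-SM score on its baseline score. Let it replace the normality-test and 10%-rule choices for the primary outcome.
2. After the last post-test, have an existing team member who neither delivers the intervention nor assesses outcomes (for example the recruitment assistant, if that is a different person from the results assistant) renumber participants, label the arms A and B and keep the key.
3. Run and date the primary analysis on that file, preferably by someone not involved in delivery if one is already on the team. Only then break the code. If no such person is available, step 1 still controls the error rate.
4. Delete the statement that the analysis cannot be masked. Keep it for delivery.

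The cost is a short document and one recoding step, with no change in sample size. The remaining weakness is that the arms may still be guessed if the effect is large or the investigator recognises participants.

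### The 20% sample addition is listed as a control for attrition bias but protects power only, and nothing in the plan deals with the loss still expected

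*Combined protocol and SAP*

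**What the plan says.** The attrition-bias entry in BIAS CONTROL, Internal validity, gives two measures. The first is preventive: "The collection of the information will be meticulous in order not to lose any data". The second is numerical: "a percentage addition will be made in the calculation of the sample to predict the mortality of the participants". The entry on selection and performance bias in the same section mentions the 20% again and adds that extensive contact details will be taken so that participants stay in follow-up.

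The SAMPLE section states that "a mortality of 20% of the participants is expected" and raises 82 (41 per group) to 100 (50 per group). Mortality here is read as loss to follow-up, since the bias section speaks of losses in the groups.

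APPROACH TO THE ANALYSIS FRAMEWORK is the only analysis text. It plans parametric or non-parametric group comparisons, chosen after a normality test, and a regression model adjusted for possible confounders. The confounders named in STUDY VARIABLES are age, gender, education, time since diagnosis and other comorbidities. Neither section names an analysis population, a missing-data method, a sensitivity analysis or the baseline score as a covariate.

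**The concern.** This is more than an omitted detail. The plan names a method for attrition bias, and that method cannot do what its heading claims. Extra recruits replace the number of people lost, not the kind of people lost. Careful collection and good contact details may reduce loss, but the plan still expects one participant in five to go, and it says nothing about how that loss enters the analysis.

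A two-group test on the week-16 score needs a week-16 score, so anyone without one drops out by default. Unequal loss is plausible here. Only the intervention arm has two 60-minute sessions, goal setting and calls at weeks 4 and 12. Its last session falls at week 16, the time of the post-test, so a person who stops the sessions may also miss the outcome. The main investigator delivers the intervention, is not blinded and takes part in the analysis. That is a further reason to fix the handling of missing scores before data are seen.

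**Working it through.** **1. The plan's own figures.** Inputs from SAMPLE: "assuming a power of 80%, a confidence level of 95%, an expected mean difference of 18.13 in the improvement of self-management", for a "comparison of means in independent groups". METHODOLOGY gives "one-to-one allocation in two parallel groups". No SD is stated.

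- Inflation: 41 × 1.2 = 49.2, rounded up to 50 per group, or 100 in total. This reproduces the plan. Dividing instead gives 82 / 0.8 = 102.5.
- SD (assumption, back-solved): n per group = 2(1.960 + 0.842)² SD² / 18.13². This gives 41 when SD is 28.9 to 29.3, two-sided. A one-sided 5% test, which the directional "H1: G1 > G2; p < 0.05" might suggest, gives 32.6 to 33.0. I use 29, two-sided.
- Check: 2 × 2.802² × 29² / 18.13² = 40.2, rounded up to 41.

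**2. What the addition achieves.** After 20% loss, 100 × 0.8 = 80, or 40 per group. Power (normal approximation) = Φ(18.13 / (29√(2/n)) − 1.960).

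- n = 41: Φ(2.831 − 1.960) = 80.8%.
- n = 40: Φ(2.796 − 1.960) = 79.8%.

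Power is almost fully kept. No term in this calculation concerns who is lost.

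**3. Size of a bias, if there is one.** Assume no true effect, 20% loss per arm, and loss related to outcome in the intervention arm only. Then bias = 0.20 × (mean of completers − mean of those lost). A gap of 0.5 to 1.0 SD gives 0.1 to 0.2 SD, or 2.9 to 5.8 points at SD 29. With 40 completers per arm, the noncentrality is bias × √(40/2), with 78 df and critical t 1.991:

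- 0.1 SD: 0.447, rejection rate 7.3%.
- 0.2 SD: 0.894, rejection rate 14.3%.

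These rates depend only on SD units. The unstated SD affects only the conversion to points.

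**4. When bias arises and when it does not.** Simulated null trials, 50 randomised per arm, 20% overall loss, logistic dropout on the week-16 score, two-sided t-test on completers:

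| Loss mechanism (assumed) | Bias, points | False-positive rate |
|---|---|---|
| Unrelated to outcome | 0 | about 5% |
| Related to outcome, identical in both arms | 0 | about 5% |
| 30% vs 10%, log-odds −1 per SD in both arms | 4.7 | 11% |
| 20% per arm, log-odds −1 per SD, intervention arm only | 5.0 | 12% |
| 20% per arm, log-odds −2 per SD, intervention arm only | 7.6 | 23% |

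**5. Loss that depends on the baseline score.** Null trials, 50 randomised per arm, 20% loss per arm, loss dependent on baseline in the intervention arm only (log-odds −0.7 to −2 per SD), baseline to week-16 correlation 0.5 to 0.7, SD 29:

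- Unadjusted post-test comparison: bias +1.8 to +5.5 points, error about 6 to 13%.
- Change-score comparison: bias −1.1 to −3.8 points, against the intervention, error about 6 to 9%.
- Week-16 score adjusted for baseline: no bias, error about 5%.

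I re-ran this mechanism at log-odds −1 and −2 and obtained the same pattern.

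**The case against.** The strongest reply is that the documents do not show any bias. Expecting 20% loss says nothing about whether loss differs between arms in a way tied to outcome. If it is unrelated to outcome, or related identically in both arms, the null comparison is unbiased. The intervention's burden is modest: two 60-minute sessions and two calls of 20 to 30 minutes over 16 weeks. Controls could leave as readily. All of this stands, which is why every bias figure above is conditional.

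Preventing loss is also a genuine control of attrition bias, and the plan has two preventive measures: careful collection and contact details. That stands too, but they do not reach the loss that is still budgeted.

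A reader might go further and infer any of the following. The documents do not support them.

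- *That the plan commits to a completers-only analysis.* It does not say so. This is the default that its tests lead to when nothing else is specified.
- *That any bias must favour the intervention.* The plan speaks both of changes and of group comparisons. Under baseline-dependent loss the sign reverses between post-test and change scores.
- *That the larger sample makes the false-positive rate materially worse.* This needs a bias to exist first. The plan's own addition then moves completers only from about 33 per arm (41 × 0.8 = 32.8) to 40. For a bias of 0.1 to 0.2 SD, the rate goes from 6.9–12.6% to 7.3–14.3%, a rise of 0.4 to 1.7 percentage points. That is no reason to recruit fewer.

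**Conclusion.** The concern holds in a limited form. Sample inflation is listed as a control for attrition bias, and it protects power only. With 20% loss expected, the plan has no stated analysis population, no missing-data method and no baseline adjustment to deal with that loss. Whether the result would in fact be biased cannot be known from the documents. It depends on loss being related to outcome differently in the two arms.

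Under that assumption, a bias of 0.1 to 0.2 SD gives 7 to 14% two-sided error instead of 5% at 40 completers per arm. At the back-solved SD of 29 this is 2.9 to 5.8 points, or 16 to 32% of the planned difference (2.9 / 18.13 and 5.8 / 18.13). Stronger selection would give more, and non-differential loss would give none. The direction is not fixed, because the plan does not settle whether post-test or change scores are compared. The point should be corrected before the analysis. It does not undermine the design or the sample size.

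**What to change.** - In the attrition-bias entry, describe the 20% addition as protecting power, and keep it.
- State that all randomised participants are analysed in the arm assigned.
- Seek the week-16 post-test from everyone, including those who stop the sessions.
- Make the primary analysis a likelihood-based repeated-measures model with the baseline and week-16 scores, to which every participant with a baseline score contributes. This removes the bias if loss depends on the observed baseline score. It does not do so if loss depends on the unseen week-16 score.
- For that second case, add one delta-shift sensitivity analysis: make the missing intervention-arm scores progressively worse until the conclusion changes, and report that value. With 20% missing in that arm, each point of shift moves its mean by 0.20 points.
- Report loss by arm.

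The cost is a little more analysis work, follow-up attempts that the plan's contact-detail measure already foresees, and possibly a less favourable estimate. No extra participants or visits are needed.
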